8.1.3.6. Composite Endpoints

The following composite endpoints (after 26 weeks of treatment) will be analyzed as secondary efficacy endpoints:

- Percentage of subjects achieving $\text{HbA}_{1c} < 7.0\%$ without weight gain
- Percentage of subjects achieving $\text{HbA}_{1c} < 7.0\%$ without severe or documented symptomatic hypoglycemia
- Percentage of subjects achieving $\text{HbA}_{1c} < 7.0\%$ without weight gain and without severe or documented symptomatic hypoglycemia

No weight gain is defined as ≤ 1 kg increase from baseline in body weight. These composite endpoints will be analyzed and summarized in a similar manner as specified in Section 8.1.2.2.

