4.5. Withdrawal Criteria

Every effort should be made to keep subjects in the study. The reasons for subjects not completing the study will be recorded.

The following **will** require withdrawal from the study:

- AE, which, in the opinion of the investigator precludes effective participation of the subject or poses a safety concern
- Elevation of liver function test results meeting any of the liver stopping criteria (see Section 6.3.6)
- Severe allergic/hypersensitivity reaction that is considered by the investigator to be attributable to randomized study medication or without a likely alternative etiology (see Section 6.3.9.3)
- Confirmed acute or chronic pancreatitis (see Section 6.3.9.4)
- Confirmed medullary thyroid cancer (see Section 6.3.9.6)
- Recurrent severe hypoglycemia or recurrent nocturnal hypoglycemia during the Treatment Period posing a potential risk to the subject, as judged by the investigator
- Pregnancy or intention of becoming pregnant
- Major protocol deviation if withdrawal from the study is mandated by the medical monitor (the investigator should discuss the protocol deviation with the medical monitor before withdrawing study medication)
- GSK-defined Sentinel Event. The medical monitor will advise the investigator if an SAE meets the criteria of a true Sentinel Event (e.g., without a clear alternate etiology) for which withdrawal is required (see Section 6.3.7.3)

In addition, a subject may be withdrawn from the study for the following reasons:

- FPG >270 mg/dL (15.0 mmol/L) at least 8 weeks after randomization on 3 consecutive days (by blood glucose meter), which is confirmed by a central laboratory (to be done within 2 weeks of the home glucose monitoring). Continuation of the subject will be at the discretion of the investigator after consultation with the medical monitor
- Lost to follow-up
- Study closed/terminated or investigator site closed (where subject transfer to another site is not possible)
- Subject decision (reason to be documented in the electronic case report form [eCRF], if specified by the subject)
- Investigator discretion

Note: Use of a prohibited medication constitutes a protocol deviation. Continuation of the subject in the study will be discussed with the medical monitor, and the decision of continuation or withdrawal will be documented.

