8.3.3.2. Other Comparisons of Interest

A key secondary endpoint is the proportion of subjects treated with once-weekly albiglutide that are able to replace prandial insulin without the need for re-introduction of insulin lispro. The 95% confidence interval of the sample proportion will be estimated, stratified by region, age category, and current use of metformin.

The proportion of subjects with hypoglycemia, as confirmed by plasma glucose monitoring <70 mg/dL (<3.9 mmol/L) and/or requiring third-party intervention through Week 26, will be compared between treatment groups, adjusting for baseline HbA_{1c} stratum, age group, current use of metformin, and region.

Other binary secondary endpoints, such as the proportion of subjects achieving HbA_{1c} treatment goals at Week 26 and the proportion of subjects achieving composite secondary endpoints (i.e., criteria involving HbA_{1c} target and hypoglycemia) will be analyzed analogous to the proportion of subjects with hypoglycemia.

Continuous secondary endpoints, e.g., changes over time in HbA_{1c}, FPG, and body weight, changes in daily insulin dose, changes in mean daily blood glucose based on 8-point SMBG, and changes in total number of weekly insulin injections will be summarized descriptively and analyzed using an MMRM (observed data). In the MMRM for non-HbA_{1c} endpoints, the corresponding baseline variable will be modeled as a covariate (in place of baseline HbA_{1c}) for variance reduction and to adjust for any baseline differences in treatment groups attributable to chance as well as the randomization stratification variables (HbA_{1c} stratum, age category, current use of metformin).

The number of hypoglycemic events with confirmed home blood glucose monitoring <70 mg/dL (<3.9 mmol/L) and/or requiring third-party intervention in 3-month intervals (i.e., from Baseline/Randomization to Week 12, >Week 12 to Week 26) will be compared between the treatment groups using a Poisson regression model with offset for the person-year, which will include treatment effect and covariates such as HbA_{1c} stratum, age (<65 years versus ≥65 years), current use of metformin (metformin use versus no metformin use), and region.

The time to meeting prespecified criteria for severe, persistent hyperglycemia at Week 26 will be analyzed for treatment group differences using pairwise log-rank tests within a Kaplan-Meier model.

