8. SECONDARY AND EXPLORATORY STATISTICAL ANALYSES

8.1. Secondary Efficacy Analyses

8.1.1. Overview of Planned Secondary Efficacy Analyses

The secondary efficacy analyses will be based on the Full Analysis (FA) population, unless otherwise specified.

Table 4 provides an overview of the planned secondary efficacy analyses, with full details of data displays being presented in [Appendix 14: List of Data Displays](#).

Table 4 Overview of Planned Secondary Efficacy Analyses

	Stats Analysis			Summary		Individual	
	T	F	L	T	F	F	L
Key Secondary Endpoints							
Proportion of subjects treated with once-weekly albiglutide that are able to discontinue insulin lispro at Week 4 and do not meet prespecified criteria for severe, persistent hyperglycemia through Week 26	Y			Y			Y
Percentage of subjects with severe or documented symptomatic hypoglycemia through Week 26	Y			Y			Y
Change from Baseline in body weight at Week 26 and over time	Y	Y		Y	Y		Y
Prescribed total daily insulin dose at Week 26	Y	Y		Y	Y		Y
Supportive Secondary Endpoints							
HbA _{1c} change from Baseline over time	Y	Y		Y	Y		
FPG change from Baseline at Week 26 and over time	Y	Y		Y	Y		Y
Proportion of subjects achieving a HbA _{1c} <7.0% at Week 26 and over time	Y			Y			
Proportion of subjects achieving a HbA _{1c} <6.5% at Week 26 and over time	Y			Y			
Incidence and time to meeting prespecified criteria for severe, persistent hyperglycemia at Week 26	Y	Y		Y			Y
Prescribed total daily insulin dose (total units and total units/kg body weight) at the Baseline/Randomization and Week 4, 10, and 18 visits	Y	Y		Y	Y		
Prescribed total daily basal insulin (insulin glargine) (total units and total units/kg body weight) at the Baseline/Randomization and Week 4, 10, 18, and 26 visits	Y	Y		Y	Y		

	Stats Analysis			Summary		Individual	
	T	F	L	T	F	F	L
Prescribed total daily basal insulin (insulin glargine) (total units and total units/kg body weight) at the Baseline/Randomization and Week 4, 10, 18, and 26 visits	Y	Y		Y	Y		
Prescribed total daily bolus insulin (insulin lispro) (total units and total units/kg body weight) at the Baseline/Randomization and Week 4, 10, 18, and 26 visits	Y	Y		Y	Y		
Total number of weekly insulin injections (7 days) to achieve glycemic control at Baseline/Randomization and Week 4, 10, 18, and 26	Y	Y		Y	Y		
Composite endpoints (after 26 weeks of treatment): Percentage of subjects achieving HbA _{1c} <7.0% without weight gain	Y			Y			

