8.1.2. Key Secondary Efficacy Endpoints

8.1.2.1. Proportion of Subjects Who Do Not Meet Prespecified Criteria for Severe, Persistent Hyperglycemia through Week 26

For this key secondary endpoint, subjects who do not meet prespecified criteria for severe, persistent hyperglycemia through Week 26 will be defined operationally as those subjects treated with once-weekly albiglutide that are able to replace prandial insulin without lispro re-introduction through Week 26. Note: For lispro re-introduction through Week 26 the time window is defined up to Week 25.

Proportion of subjects that are able to discontinue insulin lispro at Week 4 and do not meet prespecified criteria for severe, persistent hyperglycemia through Week 26 will be summarized descriptively for all the Albiglutide + Insulin Glargine arm subjects and for

subgroups of baseline HbA_{1c} category (<8.0%, ≥8.0%), region, (<65 years versus ≥65 years), current use of metformin (Yes, No) in the FA population. The 95% confidence interval of the proportions of subjects will be provided.

The insulin lispro that was re-introduced to albiglutide subjects will be characterized. Summary statistics for the number of injections, total dose, and time-to-re-introduction will be presented.

Additional exploratory analyses to identify potential risk factors for lispro re-introduction will be investigated. Potential risk factors include: baseline HbA_{1c}, baseline HbA_{1c} category, age, age category, metformin-use, duration of diabetes, weight, BMI, BMI category, time in insulin (at baseline), baseline HbA_{1c}, and total insulin dose at baseline. Time in insulin (at baseline) is defined as the earliest start date of prior insulin medications taken minus the date of first date of randomized study medication, plus 1.

8.1.2.2. Percentages of Subjects with Severe or Documented Symptomatic Hypoglycemia through Week 26

The percentage of subjects with severe or documented symptomatic hypoglycemia will be summarized descriptively by treatment and analyzed using a Cochran-Mantel-Haenszel (CMH) test, stratified by baseline HbA_{1c} category, region, age category (<65 years versus ≥65 years), current use of metformin (Yes, No) in the FA population.

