8.1.3.3. Proportion of Subjects Achieving HbA_{1c} <7% at Week 26 and over Time

The proportion of subjects achieving HbA_{1c} target values of <7.0% at Week 26 and over time will be summarized by treatment and visit for the FA population. The treatment comparison will be carried out using the CMH test and logistic regression model described in Section 8.1.2.2. The proportion of subjects who responded over time will also be plotted using a bar chart.

If a subject has a missing HbA_{1c} value at week 26 and the reason why value is missing is not related to efficacy or safety (e.g., procedural) and could be assumed that value is missing at random, then the value will be left as missing for calculations; if the reason why value is missing is lack of efficacy or due to safety, then this missing value will be imputed as ‘not meeting target’ and included in the denominator in the calculation of the proportion of subjects achieving target HbA_{1c} <7%.

The results with the observed data and with imputed data will be both presented as part of sensitivity analysis.

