8.1.3.4. Proportion of Subjects Achieving HbA_{1c} <6.5% at Week 26 and over Time

Proportion of subjects achieving HbA_{1c} target values of <6.5% at Week 26 and over time will be analyzed and summarized in a similar manner as specified in Section 8.1.3.3.

8.1.3.5. Incidence and Time to Meeting Prespecified Criteria for Severe, Persistent Hyperglycemia through Week 26

In this treat-to-target study design, subjects may be withdrawn if they have severe and persistent hyperglycemia. Meeting prespecified criteria for severe, persistent hyperglycemia at week 26 will be defined operationally as being withdrawn due to lack of efficacy as recorded on the Treatment Discontinuation and Study Conclusion eCRF pages. Proportion of subjects who meet prespecified criteria for severe, persistent hyperglycemia at Week 26 will be summarized and analyzed in a same manner as described in Section 8.1.2.2.

The time to meeting prespecified criteria for severe, persistent hyperglycemia through Week 26 will be calculated as the number of days between the date of first dose of randomized study medication and the date of meeting prespecified criteria, persistent hyperglycemia, plus 1. Subjects who do not meet the criteria will be censored at the date of the Week 26 visit or the date of the early termination visit if the subject terminated the study early. Kaplan-Meier estimates of the median time to meeting the criteria and 95% confidence interval for each treatment group will be presented. The treatment difference will be assessed using a log-rank test. The proportion of subjects meeting the criteria up to Week 26 (Day 182) based on Kaplan-Meier estimates will be displayed in the summary table. Kaplan-Meier curves of the times to meeting the criteria for each treatment group will be presented.

The analysis will be performed on FA population and all data will be listed.

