11.6.3.2. Reasons for Withdrawal

Reasons for withdrawal are assumed to fall into three broad categories:

- Procedural (i.e. lost to follow-up, investigator site closed, withdrew consent, protocol deviation, and investigator discretion that are not related to study treatment): In this case, it is expected that an assumption of missing at random (MAR) is appropriate for imputation of HbA_{1c} data after withdrawal.
- Safety (i.e. AE; subject reached protocol-defined stopping criteria; withdrew consent, protocol deviation, and investigator discretion that are related to study treatment): It is expected that, in most cases, any change in safety related to these reasons for withdrawal would have been captured prior to the subject withdrawing from the study. In Study GLP108486 (albiglutide versus lispro over background glargine), 5% of subjects in the albiglutide group and <1% in the lispro group had AEs leading to withdrawal of active treatment through Week 26. In the albiglutide group, the most common AE leading to withdrawal was injection site reaction (1.1%). Missing HbA_{1c} values after withdrawal due to safety concerns will be considered to possibly be missing not at random (MNAR).

- Lack of efficacy: In this treat-to-target study, a substantial number of cases of withdrawal due to lack of efficacy is not expected. Missing HbA_{1c} values after withdrawal due to lack of efficacy are considered to possibly be MNAR.

Sensitivity analyses will be performed for data missing due to safety concerns or due to lack of efficacy.

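### The HbA1c composite endpoints have no rule for a missing Week 26 HbA1c, so their denominator is undefined and out of step with the single-target endpoint

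*SAP*

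**What the plan says.** SAP 8.1.3.6 defines three composites after 26 weeks: HbA1c below 7.0% without weight gain, without severe or documented symptomatic hypoglycemia, and without either. On method it says only: "These composite endpoints will be analyzed and summarized in a similar manner as specified in Section 8.1.2.2". SAP 8.2.8 sends the exploratory composite (HbA1c below 7.0%, no weight gain, no glucose below 56 mg/dL) to the same section.

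That section gives this: "The percentage of subjects with severe or documented symptomatic hypoglycemia will be summarized descriptively by treatment and analyzed using a Cochran-Mantel-Haenszel (CMH) test", stratified, in the full analysis (FA) population, with supportive logistic regression. It has no rule for a missing HbA1c. Protocol 8.3.3.2 adds none; it says the composites "will be analyzed analogous to the proportion of subjects with hypoglycemia".

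For HbA1c below 7.0% alone, SAP 8.1.3.3 does have a rule: "if the reason why value is missing is lack of efficacy or due to safety, then this missing value will be imputed as" a failure to reach target and kept in the denominator. Values missing for procedural reasons stay missing, and both observed and imputed results are presented. Section 8.1.3.4 carries this to the 6.5% target by naming it: that endpoint "will be analyzed and summarized in a similar manner as specified in Section 8.1.3.3". The composites do not name it.

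The display list in SAP 11.14.4 follows the same split. Tables 2.86 and 2.87 take account of missing HbA1c for the two single targets. Composite Tables 2.83 to 2.85 and 2.601 have no counterpart.

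**The concern.** A composite of this kind is meant to show glycemic control achieved without harm, so it matters who is counted. Two programmers could follow the SAP faithfully and arrive at different denominators. If the composites are run on observed data, as the display list suggests, a subject withdrawn for safety is a failure in Table 2.87 and absent from Tables 2.83 to 2.85.

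Hypoglycemia makes this sharper. Protocol 4.5 lists, among events requiring withdrawal, "Recurrent severe hypoglycemia or recurrent nocturnal hypoglycemia during the Treatment Period posing a potential risk to the subject" in the investigator's judgment, and stopping study medication means leaving the study. The event that decides the hypoglycemia component can therefore also remove the HbA1c value. If that event was severe or documented symptomatic, the subject has failed the composites in Tables 2.84 and 2.85 whatever the HbA1c would have been. No text says how to score such a subject.

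**Working it through.** **Plan's own figure.** No rate or sample size is stated for the composites; the planned denominators come from SAP 11.12 (margin 0.3, SD 1.2, true difference 0, one-sided 0.025, 90% power).

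- n per arm = 2 × (1.960 + 1.282)² × 1.2² / 0.3² = 336.2, so 337.
- 337 / 0.85 = 396.5, so 397 per arm and 794 in total. Both figures reproduce.
- Planned early withdrawals or losses: 397 − 337 = 60 per arm.

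**Safety withdrawals.** SAP 11.6.3.2 reports for an earlier study that "5% of subjects in the albiglutide group and <1% in the lispro group had AEs leading to withdrawal of active treatment through Week 26". Using 5%, and 1% as the ceiling of the lispro figure: 0.05 × 397 = 19.85 (20) on albiglutide and 0.01 × 397 = 3.97 (4) on lispro.

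**Assumptions.** The completer response rate r is equal in the two arms (30% for illustration; the documents give no value), all these withdrawals lack a Week 26 HbA1c, and there are no lack-of-efficacy withdrawals. Responders per arm at r = 30%: 0.30 × 337 = 101.1.

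| Reading | Denominators (albiglutide v lispro) | Rates |
|---|---|---|
| Observed only | 337 v 337 | 30.0% v 30.0% |
| 8.1.3.3 rule | 357 v 341 | 101.1/357 = 28.3% v 101.1/341 = 29.7% |
| All FA, missing = failure | 397 v 397 | 101.1/397 = 25.5% in each |

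**Size.** Moving from observed-only to the 8.1.3.3 rule shifts the difference by 28.32 − 29.65 = −1.3 points. The standard error of the difference is √(2 × 0.3 × 0.7 / 337) = 3.5 points, so the shift is 1.33 / 3.5, about 0.4 standard errors.

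**Range.**
- r = 10%, 20%, 40%, 50%: −0.4, −0.9, −1.8, −2.2 points.
- Safety withdrawals 10% v 1%, r = 30%: 101.1/377 − 101.1/341 = 26.8% − 29.7% = −2.8 points.
- Equal safety withdrawals: 0.
- The 5% and 1% swapped between arms: +1.3 points.

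**A partial repair that misleads.** Suppose one also counted as failures those procedural withdrawals who had an earlier hypoglycemic event, leaving event-free ones missing. Take that step alone, with 40 procedural withdrawals per arm and prior events in 30% on albiglutide and 50% on lispro (all assumed). The denominators become 337 + 12 = 349 and 337 + 20 = 357, and the rates 29.0% v 28.3%. Entry to the denominator then depends on having failed, which lowers the rates, more so in the arm with more hypoglycemia.

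**The case against.** A reader might infer that the plan excludes these withdrawals. It does not say so. SAP 8.1.1 states: "The secondary efficacy analyses will be based on the Full Analysis (FA) population, unless otherwise specified", and that population is everyone randomized. Table 2.43, a hypoglycemia display without early withdrawals, implies that the main 8.1.2.2 analysis keeps them. Read literally, the cross-reference could retain all 397 per arm. This stands: exclusion is an inference. But the hypoglycemia endpoint needs no Week 26 laboratory value, so its handling of withdrawals does not settle the composites. Scoring everyone missing as a failure would also depart from 8.1.3.3, which leaves procedural cases missing.

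A reader might also infer that exclusion favours albiglutide. The 5% versus under 1% is an earlier study's result, and Protocol 1.2 expects less hypoglycemia on albiglutide, so hypoglycemia withdrawals could push the other way. Nor do the documents say that 15% will lack a Week 26 HbA1c: 15% is early withdrawal or loss. Under SAP 11.3.3 and 11.3.4 an end-of-treatment value within 14 days of last dose is valid and can be assigned to Week 26 from study day 156. Sixty per arm is a ceiling.

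Finally, 8.1.3.3 itself presents both versions, so an observed-only composite would match Table 2.82. What is then missing is the imputed companion and a stated rule. That narrows the gap but does not close it.

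**Conclusion.** The point holds as a gap in specification. The composites in SAP 8.1.3.6 and 8.2.8 have no rule for a missing Week 26 HbA1c, the denominator is undefined and probably observed-only, and this is inconsistent with 8.1.3.3. Certain failures on hypoglycemia may go uncounted. The likely effect is modest: 1.3 points at a 30% completer rate, and 0.4 to 2.2 points at rates of 10% to 50%, given the earlier study's withdrawal rates. The sign depends on which arm loses more subjects to safety or lack of efficacy. These endpoints lie outside the testing sequence in SAP 11.10 and carry nominal p-values, so primary and key secondary conclusions and type I error control are unaffected. It should still be settled before database lock, because the composites are prespecified secondary endpoints and the SAP already contains a rule that can be reused.

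**What to change.** In SAP 8.1.3.6 and 8.2.8, apply the 8.1.3.3 rule to the composites. A missing Week 26 HbA1c or weight after a lack-of-efficacy or safety withdrawal makes the subject a non-responder who stays in the denominator. Name withdrawal for hypoglycemia explicitly as a safety withdrawal for this purpose. State the denominator, present observed and imputed results side by side, and add companion versions of Tables 2.83, 2.84, 2.85 and 2.601.

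Do not add only those procedural withdrawals who had a prior hypoglycemic event, since the denominator would then depend on outcome. If known failures among procedural withdrawals are to be counted, do it in a separate version with all missing values scored as non-response in the full FA population.

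The cost is a few sentences, four tables and slightly lower reported rates.

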8.2. Exploratory Efficacy Analyses

8.2.1. Overview of Planned Exploratory Efficacy Analyses

The exploratory efficacy analyses will be based on the FA population, unless otherwise specified.

Table 5 provides an overview of the planned exploratory efficacy analyses, with full details of data displays being presented in [Appendix 14: List of Data Displays](#).

Table 5 Overview of Planned Exploratory Efficacy Analyses

	Stats Analysis			Summary		Individual	
	T	F	L	T	F	F	L
Exploratory Endpoints							
Patient-reported outcomes to diabetes medication at Baseline/Randomization, Week 10, and Week 26: Treatment-related impact measure for diabetes (TRIM-Diabetes) questionnaire	Y			Y			Y
Patient-reported outcomes to diabetes medication at Baseline/Randomization, Week 10, and Week 26: Hypoglycemia fear survey-II (HFS-II) worry subscale	Y			Y			Y
HbA _{1c} change from Baseline at Week 26 by baseline FPG tertiles	Y			Y			Y
FPG change from Baseline at Week 26 by baseline FPG tertiles	Y			Y			Y
24-hour glucose profile: 8-point self-monitored blood glucose (SMBG) profile at Baseline/Randomization, Week 10, and Week 26 (before and 120 minutes after the 3 main meals, at bedtime, and at 2 AM)	Y			Y	Y		Y
Mean daily blood glucose based on the 8-point SMBG profile at Baseline/Randomization, Week 10, and Week 26	Y			Y			Y
Number (and percentage) of subjects with <=1 kg weight gain at Week 26	Y			Y			Y
Percentage of subjects achieving HbA _{1c} <7.0% without weight gain and without hypoglycemia with blood glucose <56 mg/dL (<3.1 mmol/L) regardless of symptoms at Week 26	Y			Y			Y
Proportion of subjects treated with once-weekly albiglutide that are able to totally replace or decrease prandial insulin without worsening HbA _{1c} control (worsening defined as >0.3% increase in HbA _{1c} compared with baseline HbA _{1c}) at Week 26	Y			Y			Y
Genetic sampling							
Novel biomarker analysis	TBD	TBD	TBD	TBD	TBD	TBD	TBD

NOTES :

T = Table, F = Figure, L = Listing, Y = Yes display generated.

Stats Analysis = Represents TFL related to any formal statistical analyses (i.e. modelling) conducted.

Summary = Represents TF related to any summaries (i.e. descriptive statistics) of the observed raw data.

Individual = Represents FL related to any displays of individual subject observed raw data.

TBD = to be determined after review of efficacy and safety data at the end of the study or other emerging information that may become available during the study

Following review of the data, additional analyses maybe conducted to further support the evaluation and interpretation of the data.

